9.4 STATISTICAL ANALYSES

9.4.1 GENERAL APPROACH

Summary statistics: Demographic and clinical data will be summarized according to treatment arm using means, S.D.s, medians, quartiles, and proportions, as appropriate. As per ICH E-9 guidelines, no inferential comparisons of the two arms will be carried out.

9.4.2 ANALYSIS OF THE PRIMARY EFFICACY ENDPOINT(S)

Analysis of the primary outcome: For the primary outcome, which we assume will be normally distributed, the two independent sample t test comparing two independent groups will be used to compare the pain scores from study arms at POD1. In the event that normal assumption does not hold, a suitable data transformation (e.g., arcsine square-root, logit) will be applied.

A 95%, two-tailed confidence interval for the difference of mean pain scores between the two arms will be constructed. If both upper and lower confidence intervals lay within the ± 1 -unit margin, we will conclude that the pain scores associated with the two routes of wound infiltration are equivalent. Otherwise, we cannot conclude that the effects between the two modes of wound infiltration on postoperative pain are equivalent.

As per ICH E-9 guidelines, a supporting analysis will be conducted whereby analysis of covariance (ANCOVA) will be used to compare the two groups, adjusting for nuisance covariates.

All continuous secondary outcomes will be analyzed using two sample t-test or Mann-Whitney test depending on whether normal assumption holds or not. ANCOVA will be used adjusting for baseline values and other associated covariates and will be considered as supportive analysis.

All categorical secondary outcomes will be analyzed using chi-square test for proportions or Fisher's exact test, as appropriate.

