1.2 SCHEMA

Visit 0

- New patient/Surgical discussion Visit
 - Screen potential for inclusion and exclusion criteria
 - If meets criteria
 - Pamphlet provided to patient in regard to study information

Visit 1

- Preoperative visit
 - Discuss study in further detail, answer questions after patient read pamphlet, risks/benefits discussed and offer patient participation
 - If patient consents:
 - First Brief Pain Inventory Questionnaire to fill out prior to surgery. The Narcotic Diary will be given to patient with the instructions to fill out after surgery and to document all narcotic pills used including provided and any additional.
 - If a patient is undecided, then will follow up by phone call prior to surgical day. If she decides after follow up phone call then will have patient sign consent on day of surgery

Visit 2

- Day of surgery

- If patient does not consent at preoperative visit, but decides to participate after follow up phone call:
 - Obtain consent if patient has agreed by phone call (phone call which is after preoperative visit) on the day of surgery
 - Provide narcotic diary and first Brief Pain Inventory Questionnaire to fill out (if patient has not already filled it out previously). Patient only needs to fill out one brief pain inventory questionnaire prior to surgery, the patient should fill this out on the day that they sign the consent for participation (whether it is at the preoperative visit or in the preoperative suite on the day of surgery). The Narcotic Diary will be given to patient with the instructions to fill out after surgery and to document all narcotic pills used including provided and any additional.
- Randomization
 - Arm 1: 64 patients; Arm 2: 64 patients

Visit 3

- Postoperative Day 1
 - Obtain Likert-pain scale score between 18-24 hours post-surgery

Visit 4

- Postoperative Visit (14 days +/- 3 days)
 - Narcotic Diary collected
 - Second Brief Pain Inventory Questionnaire given to patient to complete

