4 STUDY DESIGN

4.1 OVERALL DESIGN

- Central Objective To examine patients reported pain levels or narcotic usage between pre-incision versus post-incision subcutaneous infiltration of 4-5mL 0.25% Bupivacaine after a robotic/laparoscopic-assisted sacrocolpopexy.

Research Plan:

- Randomized, controlled, single-blinded study

Setting of the study:

- Operating room of patients undergoing robotic/laparoscopic sacrocolpopexy

Participants:

- Patients aged 18 years old and above who are scheduled to undergo robotic/laparoscopic-assisted sacrocolpopexy (with or without hysterectomy and with or without midurethral sling)

Randomization Scheme

- Randomization will be accomplished using the Biostatistics Randomization Management System
- 1:1 Randomization, permuted blocks
- Subjects will be randomized using a computer generated table into one of two groups:
 - Arm one: subcutaneous infiltration pre-incision
 - Arm two: subcutaneous infiltration post-incision
- Surgeons will be notified by e-mail of their patient allocation on day of surgery

Pre-surgery

- Consent will be obtained and the patient will be given a Brief Pain Inventory Questionnaire to complete. The Brief Pain Inventory Questionnaire is a validated medical questionnaire to measure pain. The questionnaire measures the patient's pain intensity and the amount of interference the pain has on their being able to function in their daily living.
- Intervention or experimental aspect of the study
 - General anesthesia will be given as per standard protocol
 - Preoperative pain medication will be ordered for each patient as per standard enhanced recovery protocol
 - Operative Time: Generally total of 180 – 300 minutes
 - Total dose of 0.25% Bupivacaine injection:
 - 8-10 mm incisions x 5 incisions = 20-25 mL (4-5 mL each)
 - 20-25mL of 0.25% Bupivacaine distributed over 5 trocar sites (4-5mL per incision)
 - Skin closure: subcutaneous closure with monofilament absorbable suture with 4-0 absorbable suture and fascia closure of the umbilical port site with #0 delayed absorbable suture and skin closure with 4-0 absorbable suture

- Pre-incision arm: Marcaine (bupivacaine) injected in the umbilical port site subcutaneously, while in the other 4 sites injection under direct visualization
- Post-incision arm: local anesthetic infiltrated subcutaneously at the end of the procedure after trocar removal and after skin closure with suture

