6.3 MEASURES TO MINIMIZE BIAS: RANDOMIZATION AND BLINDING

- Patient-blinded study
- Multi-site study
- The surgeon at the time of intervention will not be blinded as to which arm the patient belongs
- Randomization will be performed using 1:1 randomization, permuted blocks

Randomization will be accomplished using the Biostatistics Randomization Management System according to hospital site.

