9. STATISTICAL CONSIDERATIONS

9.1 STATISTICAL HYPOTHESES

- Primary Efficacy Endpoint(s):
 - Assessment of infiltration at pre-incision (pre) and infiltration at post-incision (post) associated pain score using a Likert-pain scale. The Likert-like pain scale is a validated, subjective measure for acute and chronic pain. The primary endpoint of pain score measurement will take place on postoperative day 1 (18-24 hr post-surgery, postoperative day 1). Scores are recorded by choosing an integer only number on a 0-10 scale that represents between “no pain” and “worst pain”.
- Secondary Efficacy Endpoint(s):
 - The need for additional narcotic usage over 2 weeks between the 2 arms
 - Compare questionnaires between the initial brief pain inventory questionnaire (pre-surgery) and postoperative brief pain inventory questionnaire

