9.4.3 ANALYSIS OF THE SECONDARY ENDPOINT(S)

Analysis of the secondary outcome:

- The need for additional Narcotic usage over 2 weeks between the 2 arms

All patients will be discharged with 12 standard narcotic pills for managing post-operative pain by needs. However, patients can request additional narcotic pain killers if needed. The needs for extra amount of pain reliever is an indicator of pain level and a secondary aim of the current study.

The need for additional narcotic usage is a binary-coded variable with values of 'yes' or 'no'. The rate/percentage of patients requesting additional narcotic medication will be calculated for each study arm, and compared in a 2 by 2 contingency table format using chi-square test or Fisher's exact test, as appropriate.

- Compare pain scores between each arm at 2 weeks post-operative visit

At the two-week post-operative visit, patients will be asked to fill out the brief pain inventory to indicate their current pain levels, as well as the mildest and worst pain scores within the past 24 hours. The pain scores will also be evaluated by Likert-pain scale (the same pain assessment tool used at POD1. The mean pain scores between the two arms will be compared by a two-sample t-test or a Wilcoxon rank-sum test, where appropriate. Statistical significance between the two arms is considered if the p-value for the tests are <0.05.

9.4.4 9.4.4 SAFETY ANALYSES

Patients will be screening for allergy to or contraindications to study medication. If they meet criteria and consent for the study, then each patient will be monitored for safety in multiple forms. For each patient, vital signs are monitored in the operating room and during recovery until discharge. Electrocardiogram monitoring will also be continuously ongoing in the operating room. Assessment of adverse events throughout hospital stay will be done by review of charts and discussion with other members involved in patient care.

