9.4.5 BASELINE DESCRIPTIVE STATISTICS

Demographic and clinical data (including operative time and procedure performed) will be summarized according to treatment arm using means, S.D.s, medians, quartiles, and proportions, as appropriate. As per ICH E-9 guidelines, no inferential comparisons of the two arms will be carried out.

All continuous secondary outcomes will be analyzed using two sample t-test or Mann-Whitney test depending on whether normal assumption holds or not. ANCOVA will be used adjusting for baseline values and other associated covariates and will be considered as supportive analysis.

All categorical secondary outcomes will be analyzed using chi-square test for proportions or Fisher's exact test, as appropriate.

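### The confidence interval that decides equivalence ignores randomisation site and baseline pain, so it is valid but may be wider than it need be

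*Combined protocol and SAP*

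**What the plan says.** **Design.** Allocation is 1:1 in permuted blocks, and section 6.3 adds: "Randomization will be accomplished using the Biostatistics Randomization Management System according to hospital site". The synopsis (1.1) lists eight hospitals. Baseline pain is collected from everyone. Section 4.1 says "Consent will be obtained and the patient will be given a Brief Pain Inventory Questionnaire to complete", and the schema (1.2) makes clear this happens once: "Patient only needs to fill out one brief pain inventory questionnaire prior to surgery".

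**Primary analysis.** In section 9.4.2, "the two independent sample t test comparing two independent groups will be used to compare the pain scores from study arms at POD1". A two-sided 95% confidence interval for the difference in means is then set against ±1, and equivalence is concluded only if both limits fall inside. In a separate supporting analysis, "analysis of covariance (ANCOVA) will be used to compare the two groups, adjusting for nuisance covariates". Those covariates are not listed.

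**Day-14 pain.** Section 9.1 describes this endpoint as "Compare questionnaires between the initial brief pain inventory questionnaire (pre-surgery) and postoperative brief pain inventory questionnaire". The main test in section 9.4.3 makes no use of the pre-surgery questionnaire: "The mean pain scores between the two arms will be compared by a two-sample t-test or a Wilcoxon rank-sum test, where appropriate". For continuous secondary outcomes generally, sections 9.4.2 and 9.4.5 say "ANCOVA will be used adjusting for baseline values and other associated covariates and will be considered as supportive analysis".

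**The concern.** Site is built into the randomisation and baseline pain is already on file, yet the interval that decides the trial's main conclusion uses neither. If either predicts POD1 pain, variation that could be removed stays in the standard error. The margin leaves little room for this. With a half-width near 0.70, equivalence requires an observed difference within about ±0.30, so a modest narrowing bears directly on the conclusion.

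The supporting ANCOVA does not fill the gap. It does not decide equivalence, its covariates could be chosen after the data are seen, and there is no rule for the case where the two analyses fall on different sides of the margin.

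**Working it through.** **1. The plan's own figure.** Section 9.2 gives difference 1, SD 2, two-sided alpha 0.05, power 0.80, equal arms and no dropout. The noncentral t calculation gives power 0.795 at 63 per arm and 0.801 at 64. The stated 64 per arm reproduces.

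**2. The deciding interval as planned.** Half-width = t(0.975, 126) × SD × √(2/n) = 1.979 × 2 × √(2/64) = 0.700. The observed difference must therefore lie within 1 − 0.700 = 0.300 of zero. With SE = 2 × √(2/64) = 0.354 and a true difference of 0, the probability of concluding equivalence is about 2Φ(0.300/0.354) − 1 = 0.60. Integrating over the sampling distribution of the SD gives 0.603.

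**3. What adjustment could do in principle.** If site and baseline pain together explain a fraction R² of the variance, the residual SD is 2√(1 − R²). R² is an assumption, because the documents give no value. Eight degrees of freedom are charged in the adjusted rows (seven for eight sites, one for baseline).

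| R² | Half-width | P(equivalence), true difference 0 |
|---|---|---|
| 0 (t-test) | 0.700 | 0.60 |
| 0.05 | 0.682 | 0.64 |
| 0.10 | 0.664 | 0.68 |
| 0.20 | 0.626 | 0.76 |
| 0.30 | 0.586 | 0.84 |

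**4. Simulation with blocks within site.** There were 10,000 trials per setting, with N = 128, total SD 2 and true difference 0. The t-test was compared with an ANCOVA on site and baseline. Site share of variance, baseline correlation r, patients per site and block size are all assumptions. Eight sites of 16, blocks of 4:

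| Site share | r | Half-width, t-test → ANCOVA | P(equivalence), t-test → ANCOVA |
|---|---|---|---|
| 0 | 0 | 0.699 → 0.702 | 0.606 → 0.599 |
| 0.02 | 0.1 | 0.697 → 0.691 | 0.612 → 0.622 |
| 0 | 0.2 | 0.698 → 0.687 | 0.606 → 0.630 |
| 0.05 | 0.2 | 0.696 → 0.669 | 0.622 → 0.667 |
| 0.05 | 0.3 | 0.696 → 0.651 | 0.618 → 0.704 |
| 0.10 | 0.3 | 0.695 → 0.632 | 0.628 → 0.744 |

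**5. Less tidy conditions.** The first, second and fifth settings above were repeated with unequal sites (44, 28, 20, 12, 10, 6, 5 and 3 patients, those under 8 pooled):

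- Blocks of 4: 0.602 → 0.592, 0.610 → 0.616, 0.612 → 0.704.
- Blocks of 6: 0.595 → 0.585, 0.609 → 0.614, 0.620 → 0.700.
- Skewed integer 0–10 score, blocks of 4 (mean about 1.8 and SD about 2, in line with section 9.2): 0.593 → 0.585, 0.598 → 0.603, 0.603 → 0.668. In the last of these, r = 0.3 on the latent scale became 0.26 on the observed score.

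**6. Validity.** ANCOVA coverage was 94.6% to 95.5% in all these settings. In a separate run of 5,000 trials per setting, with site shares up to 20%, coverage of the unadjusted interval was 94.7% to 97.2%, rising with the site share. With a true difference of 1, it declared equivalence in 1.5% to 2.6% of trials, against a nominal 2.5%. The t-test interval is therefore sound, and conservative when site matters.

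**7. Day 14.** Adjusting for a baseline with correlation r narrows the interval by 1 − √(1 − r²): 0.5% at r = 0.1, 2% at 0.2, 4.6% at 0.3 and 13% at 0.5.

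**The case against.** An unadjusted primary analysis with ANCOVA in support is a legitimate choice, and it matches the t-test used for the sample size. Nothing in the plan is invalid. That stands, and the point is one of efficiency only.

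The gain may be small. Section 5.2 excludes chronic pain syndromes and fibromyalgia, and section 6.5 standardises analgesia. The POD1 score is taken at least 1.5 hours after any pain medication (4.1). The inventory is a different instrument, completed on whichever day the patient consents (1.2). All of this could weaken prediction, although none of it shows that the correlation is negligible. The larger gains appear only at assumptions the documents neither support nor exclude. The argument for change is therefore the asymmetry: about 1 point lost if the covariates are useless, several gained if they are moderately useful.

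The low probability of concluding equivalence comes mainly from sizing the trial for a difference test. That also stands; adjustment does not cure it.

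On day 14, the synopsis and section 3 define the endpoint as a between-arm comparison, so section 9.4.3 implements that definition and section 9.1 is the outlier. The unadjusted test therefore does not miss its endpoint. What remains is that the baseline-adjusted analysis, already planned, is the more precise one.

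Finally, section 6.3 does not use the word stratified. Randomising according to site is most naturally read that way.

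**Conclusion.** The concern holds. The deciding interval is valid but is wider than necessary to the extent that site or baseline pain predicts POD1 pain. At SD 2 and a true difference of 0, moving to the adjusted interval changes the probability of concluding equivalence by about −1 point if neither predicts. The change is about +0.5 to +1 point at 2% site variance and r = 0.1, and about +6.5 to +9 points at 5% and r = 0.3. Site share, r, site sizes and block size are assumptions.

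Adjustment should not be relied on to reach 80%: in the table in step 3, that would need R² somewhere between 0.20 and 0.30. The change should be made because it is cheap and its downside is small. Confidence in the size of the gain is only moderate.

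**What to change.** - **Primary endpoint.** In section 9.4.2, take the estimate and the deciding 95% interval from an ANCOVA of the 0–10 POD1 score, the scale on which the ±1 margin is set. Include treatment, randomisation site and one named baseline inventory item, for example current pain. Keep the t-test as the supporting analysis.
- **Rules fixed in advance.** Pool sites with fewer than 8 randomised patients into one stratum. Replace a missing baseline value by the mean over both arms. These are suggested conventions; what matters is that they are set before the data are seen.
- **Day 14.** Make the baseline-adjusted ANCOVA the main comparison, and keep the t-test or rank-sum test of section 9.4.3 as a sensitivity analysis.

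The cost is SAP wording, with no new data, visits or patients. The model uses up to 8 degrees of freedom. If neither covariate is prognostic, the interval is about 0.4% to 0.7% wider and the probability of concluding equivalence falls by about 1 point.

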2 INTRODUCTION

2.1 STUDY RATIONALE

Pelvic organ prolapse is becoming more common as women's life expectancy is increasing and the prevalence of obesity is rising. Many women undergo pelvic reconstructive surgery to treat their prolapse and improve their quality of life. The incidence of pelvic organ prolapse is 1.5-1.8 surgeries per 1,000 women years (1). Approximately 300,000 pelvic reconstructive surgeries are performed each year in the United States (1). There is a wide variety in surgical approaches and procedures for prolapse. One such procedure is a sacrocolpopexy in which the cervix or vaginal cuff is lifted to the anterior longitudinal ligament overlying the sacrum via a mesh graft. This can be done in a minimally invasive fashion with a laparoscopic or robotic approach or in an open abdominal approach. Numerous studies have shown this procedure to have a high success rate and long-term durability (2). As robotic/laparoscopic approach to surgery has shown shorter hospital-stays and improved patient outcomes, the robotic-assisted sacrocolpopexy has been rapidly incorporated into clinical practice (2).

In general, surgery causes a release of painful chemical mediators which has led to increased narcotic use, increased narcotic addiction, and number of pills prescribed. Most individuals who undergo surgery will require narcotics postoperatively to control their pain and some individuals have to extend their hospital stay until adequate pain control is achieved. Our study is aimed to reduce narcotic use, decrease hospital stay due to pain issues and determine if timing of adjunct pain medication improves pain scales for patients.

As postoperative pain after minimally invasive surgery is complex, specialists suggest that the effective analgesic treatment should be a multimodal approach (4). Use of local anesthetic with bupivacaine at robotic/laparoscopic trocar sites is the standard of care, however, there is no standard as to optimal timing that is most beneficial for patients to decrease pain. Currently, bupivacaine is used by providers at the trocar sites at either the beginning of the case or at the end of the case. From clinical

observation, it appears that postoperative pain levels reported from patients receiving either at the beginning of surgery (pre-) or end (post-incision) of the surgery are similar. This study aims to examine the difference in POD1 pain levels reported by patients between the two infiltration methods.

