3 OBJECTIVES AND ENDPOINTS

OBJECTIVES	ENDPOINTS	JUSTIFICATION FOR ENDPOINTS
Primary Difference in Likert-pain scale score difference between pre-incision versus post-incision subcutaneous infiltration with 4-5mL 0.25% Bupivacaine at 18-24 hours postoperatively	Likert-pain scale score difference between pre-incision and post-incision subcutaneous infiltration at 18-24 hours postoperatively.	To determine if timing of local anesthetic affects postoperative pain scores.
Secondary To compare total narcotic usage over two weeks	Total number of narcotic tablets used in the first two weeks postoperatively between pre-incision and post-incision subcutaneous infiltration with 4-5mL 0.25% Bupivacaine	To decrease postoperative narcotic usage
Secondary Compare brief pain inventory questionnaire survey score	To compare score levels of the brief pain inventory questionnaire at POD14 between the two study groups	To decrease pain score for patient post surgery

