9.2 SAMPLE SIZE DETERMINATION

We used pain score measured at POD1 as our primary outcome of interest. Sample size calculation was calculated using two independent sample t test, under the assumption that the pain scores are normally distributed. At the following test settings:

H_{null} : Mean difference of pain levels reported on a Likert-pain scale by patients between pre- and post-incision arms at POD1 = 0;

H_a : Mean difference of pain levels reported on a Likert-pain scale by patients pre- and post- incision arms at postoperative day one $\neq 0$, and the expected mean difference of pain levels between the two groups is 1 likert point*.

Further we assume,

Standard deviation (std) = 2;

With the following default set-up values:

Alpha = 0.05

Power = 0.8

Weight between study arms = 1 (equal sample size in each arm)

Drop-out rate = 0

The required sample size for the current study is **64 per arm or 128 in total**.

*No well-established mean difference between the two study groups can be found in the literature. Based on clinical observations and experience from physicians that the two different infiltration methods are currently used interchangeably with no obvious difference in patients reported POD1 pain, we hypothesize the likely difference of pain levels between the two study groups to be 1. With standard deviation of 2 (see below), our targeted effect size is 0.5, or a median size effect based on Cohen's rule (Cohen, 1989).

**This SD value was estimated from the study by Yeung et al. (Liposomal Bupivacaine During Robotic Colpopexy VOL. 131, NO. 1, JANUARY 2018) using data from Table 3, average pain with rest at POD1 for the Bupivacaine group. Yeung et al. showed that the mean pain level with rest at POD1 in patients treated with liposomal Bupivacaine was 18.0, with the range of data being 81, on a 100mm-VAS scale. Therefore, a 'rule-of-thumb' of estimating standard deviation: range of data/4 was taken, yielding sd of ~20mm on a VAS scale. This was further translated to a sd of 2 on a 10-point Likert scale as one of the parameters for the sample size calculation for the current study.

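### The trial is sized to detect a 1-point difference, but the only primary conclusion written out is equivalence within ±1, whose power is not stated (about 60% at best at the plan's SD of 2)

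*Combined protocol and SAP*

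**What the plan says.** Section 9.2 sets a null hypothesis of zero mean difference in day-1 pain against a two-sided alternative. On the method it says "Sample size calculation was calculated using two independent sample t test", and on the effect, "the expected mean difference of pain levels between the two groups is 1 likert point". With SD 2, alpha 0.05, power 0.8, equal allocation and no drop-out, it arrives at 64 per arm. Its footnote argues from clinical experience: "no obvious difference in patients reported POD1 pain, we hypothesize the likely difference of pain levels between the two study groups to be 1".

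Section 9.4.2 names the two-sample t test for the primary outcome but does not say what follows from its result. It then calls for a two-sided 95% confidence interval. If both limits lie within ±1 point, "we will conclude that the pain scores associated with the two routes of wound infiltration are equivalent". The next sentence covers every other result: "Otherwise, we cannot conclude that the effects between the two modes of wound infiltration on postoperative pain are equivalent".

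Section 9.1, despite its title, describes the endpoint ("associated pain score using a Likert-pain scale") and states no hypothesis. The justification in Section 3 is "To determine if timing of local anesthetic affects postoperative pain scores", and Section 2.1 says "This study aims to examine the difference in POD1 pain levels reported by patients between the two infiltration methods". The 0.05 p-value criterion in Section 9.4.3 is written for the two-week pain scores only.

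**The concern.** A test for a difference and a rule for equivalence answer different questions and have different power. The stated 80% belongs to the t test, for which no primary conclusion is written. The rule that does carry a written conclusion has no stated power.

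Section 9.2 also calls 1 point the expected difference, while Section 9.4.2 uses 1 point as the equivalence margin. If the planning assumption is true, the written rule is bound to fail almost always.

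The headline conclusion is at stake. Two success criteria sit side by side and neither is ranked first, so the choice between them could be made after the data are known. A reader who takes the 80% as the chance of a clear answer from the written rule would be misled.

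**Working it through.** **Inputs.** From Section 9.2: 64 per arm, SD 2, two-sided alpha 0.05, planned difference 1, no drop-out. From Section 9.4.2: 95% interval, margin ±1. The plan gives no true difference for the equivalence rule. I take 0 as the most favourable case and show 0 to 1.

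**1. The plan's own figure.** The standard error of the difference is 2 × √(2/64) = 0.3536. The noncentrality is 1/0.3536 = 2.83 on 126 degrees of freedom. The noncentral t distribution gives power 0.8015 at 64 per arm and 0.7952 at 63. So 64 per arm is right for the difference test.

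**2. What the equivalence rule requires.** The expected half-width of the 95% interval is t(0.975; 126) × 0.3536 = 0.6997. For the interval to lie inside ±1, the observed difference must be within about 1 − 0.70 = 0.30 of zero.

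**3. Chance of concluding equivalence.** With the SD treated as fixed, the chance at true difference 0 is 2Φ(0.3003/0.3536) − 1 = 2Φ(0.849) − 1, or about 0.60. Integrating over the sampling distribution of the pooled variance gives 0.603. The same integration at SD 2 gives:

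| True difference | 0 | 0.25 | 0.5 | 0.75 | 1 |
|---|---|---|---|---|---|
| Equivalence concluded | 60.3% | 49.7% | 27.7% | 10.3% | 2.5% |

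**4. Sensitivity to the SD.** Section 9.2 takes the SD from a published range divided by 4 (81/4, about 20 mm on a 100 mm scale, rescaled to 2 points). At true difference 0:

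| SD | 1.5 | 1.75 | 2 | 2.25 | 2.5 |
|---|---|---|---|---|---|
| Equivalence concluded | 92.5% | 78.8% | 60.3% | 40.7% | 22.5% |

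Missing day-1 scores lower the chance further. At SD 2 and true difference 0 it is 56.4% with 61 evaluable per arm and 52.2% with 58.

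**5. How the two criteria combine.** From 2,000,000 simulated trials at SD 2:

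| True difference | Equivalent | Significant t test | Neither |
|---|---|---|---|
| 0 | 60% | 5% | 35% |
| 0.5 | 28% | 29% | 43% |
| 1 | 2.5% | 80% | 17% |

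**6. A 90% interval, and the size for 80%.** With a 90% interval (two one-sided tests at 0.05), 64 per arm gives 75.7% at true difference 0. For 80% at true difference 0, the normal approximation is n = 2 × SD² × (z₁ + z₀.₉₀)²/margin².
- 95% interval: 8 × (1.960 + 1.282)² = 84.1. The exact calculation gives 86 per arm (0.806; 85 gives 0.7998).
- 90% interval: 8 × (1.645 + 1.282)² = 68.5. The exact calculation gives 70 per arm (0.806; 69 gives 0.7985).

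**The case against.** The strongest reply is that this is a difference trial. Section 9.2 gives the null, the alternative, alpha and the test; Section 9.4.2 names that same test first; and most of the objectives ask about a difference. On that reading the 80% is properly attached, and the interval rule is an added interpretation without power of its own. The reading is reasonable, and it is why I do not fault the sample size. But the plan never says so. Section 9.4.2 writes a conclusion for the interval and none for the t test, and does not say which governs.

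Three further points are fair:
- A 2.5% chance of declaring equivalence when the truth lies on the margin is the rule's intended error rate. One threshold can serve both as the difference to detect and as the margin. The difficulty is only that Section 9.2 calls that value the expected difference.
- The 60% is a maximum over the true difference, not over the SD. At SD 1.75 the chance is 78.8%, close to 80%.
- The rule is conservative. Low power leads to failure to conclude equivalence, not to false claims of it, and the cautionary sentence guards against reading a non-significant test as proof of sameness.

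These points limit the finding to the decision rule. They do not supply the missing ranking or the missing power.

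**Conclusion.** The concern holds. The sized hypothesis and the written primary decision rule do not match, and the documents give no power for that rule. With 64 evaluable per arm, normally distributed scores and SD 2, its power is at most 60.3%, reached at true difference 0.

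If the two timings truly give the same mean pain, which Sections 2.1 and 9.2 report as the clinical impression, about 40% of trials would end unable to conclude equivalence: about 35% with neither criterion met and about 5% with a significant t test. Section 9.4.2 does not say what the primary conclusion would be in either case. The size of the shortfall depends strongly on the SD; the mismatch does not. It must be settled before outcome data are seen.

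**What to change.** Choose one primary question and make Sections 9.1, 9.2 and 9.4.2 agree.

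**(A) Difference**, as most of the objectives read. Keep 64 per arm and 80%. State in Section 9.4.2: *The primary conclusion is based on the two-sided two-sample t test at alpha 0.05; the 95% CI is reported descriptively.* Delete the two equivalence sentences. A compatible variant keeps the interval rule, labelled secondary, with its power stated (about 60% at true difference 0 and SD 2). This preserves the caution against reading a non-significant test as equivalence.

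**(B) Equivalence.** Write H0: |difference| ≥ 1 against H1: |difference| < 1 in Sections 9.1 and 9.2, and label the test of zero difference secondary. Replace the stated power with what 64 per arm delivers at true difference 0 and SD 2: about 60% with the 95% interval, or about 76% with the 90% interval if that is prespecified. Also confine the ±1 margin to the original pain scale, because it has no direct meaning after the arcsine or logit transformation that Section 9.4.2 allows.

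**Cost.** The change is a wording amendment, with the ethics board approval that the Statement of Compliance requires, and no extra patients under (A) or under (B) at 64 per arm. Under (B) the stated power becomes less favourable. Restoring 80% under (B) is optional: 86 − 64 = 22 more per arm (44 in total) with the 95% interval, or 70 − 64 = 6 more per arm (12 in total) with the 90% interval. Any such increase would have to be weighed against the planned 18-month duration.
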